1.5 Data Sharing

As a member of the International Stroke Genetic Consortium, Wake Forest collaborates to identify medical, environmental and genetic risk factors and causes of stroke to better care for our patients.

The Ethnic/Racial Variations of Intracerebral Hemorrhage (ERICH) study originally recruited over 3000 cases of spontaneous hemorrhage with equal power among white, black and Hispanic cases. ERICH-Gene will combine additional ICH cases from around the world to maximize the power of our study to identify novel genetic variants across ethnicities. The new goal is to perform centralized genotyping of 5,200 new ICH cases under the ERICH-Gene Study with case harmonization of advanced clinical and neuroimaging phenotypes. These data will be de-identified prior to sharing in accordance with NIH dbGap broad data sharing regulations. De-identified data may be shared for future studies according to NIH road data sharing requirements.

Given the devastating nature of ICH and the data provided, a randomized double blinded, placebo-controlled pilot trial of fingolimod plus best standard of care management versus placebo plus best standard of care management in the treatment of ICH is justified. First, given the long half-life of fingolimod, this study will assess the safety of single dosing of fingolimod to be given to critically ill patients, considering that a large portion of patients with ICH requires a prolonged ICU stay (the rate of nosocomial infections in the ICH patient population is approximately 23.1%⁸², and the incidence of clinically significant bradycardia after the first dose has been reported in 0.5%⁶⁰). Secondly, we will explore the use of T and B cell subsets as biomarkers of drug effect in this critically ill patient population. And finally, we will be evaluating for any differences in clinical outcomes during an extended 365 day period and perihematomal edema on radiographic imaging.

Objectives:

Specific Aim #1: Assess the safety of a single dose of fingolimod in patients who present with ICH.

Hypothesis #1: We hypothesize that there will be no difference in adverse events compared with placebo, as defined by a) drug-related adverse events; b) nosocomial infections; and c) neurologic decline.

Specific Aim #2: Evaluate the use of CD4+ T, CD8+ T, and CD19+ B cells as biomarkers of drug effect in a critically ill ICH population.

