- For participants with evidence of clinical or radiographic hydrocephalus, they will undergo standard of care placement of an external ventricular drain (EVD). Unless it is emergent and needs to be placed in the emergency room as a life-saving procedure, each participant will be admitted to the Neuroscience Intensive Care Unit for expeditious placement of the EVD. Once the head is secured to the bed, the hair on the right side of the head will be clipped. Kocher's point will be identified, and incision will be marked with a skin marker. The area will be prepped steriley with Chloroprep. The procedure is then completed in the usual sterile manner for twist drill burr hole placement and the placement of the EVD. This will then be tunneled subcutaneously under the scalp away from the incision and secured. At this time, 5 cc of CSF will be collected and saved for future multi-omic analysis.
- All participants enrolled are to be placed on telemetry to monitor for any cardiac events.
- Each participant will receive neurologic assessments by 2 blinded neuroscience subspecialists on Day 1, 3, 5, 7, and 14 (discharge dependent).
- Each participant will have their vitals performed and collected as part of standard of care. Vitals will be specifically recorded at the time of their neurologic assessment by the blinded assessors.
- Each participant will be getting daily standard of care blood draws, approximately 10 cc worth of blood, until time of discharge. The standard of care studies will include CBC with differential, basic metabolic panel (BMP), and LFTs. On Day 1, 3, 5-7 (discharge dependent), these standard of care blood draws will include 5 cc of blood that will be collected for lymphocyte subset analysis for research purposes for biomarker testing. Drug response will be assessed by lymphocyte subset levels. Additionally, 10 cc of blood will also be drawn at the 30 day visit for standard of care studies

(CBC with differential and lymphocyte subset analysis, BMP), in addition to 5 cc set aside in storage for future multi-omic analysis. However, there will be no blood draws if the participant is experiencing severe anemia.

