- All adverse events to be monitored from admission until day of discharge and at all follow up visits. These will include a) clinically significant cardiac events, b) nosocomial infections, and c) neurologic decline.
 - Clinically significant cardiac events: All subjects will be placed on telemetry for 72 hours after administration of drug and changes in heart rate or rhythm will be recorded. Maximal decrease in heart rate occurs within 6 hours of drug administration and recovers, with only 0.5% of patients experiencing clinically symptomatic bradycardia.⁶⁰
 - Nosocomial infections: All UTI, sepsis, and pneumonia events will be recorded and compared to published ICH nosocomial infection rates (23%).⁸²
 - Neurologic decline: Throughout hospitalization, all subjects will be monitored for neurologic decline, which has been reported to occur in up to 33% of patients within the first 48-72 hours.⁸³ Each subject will be assigned a GCS score and NIHSS score at time of enrollment, Day 1, 3, 5, 7, and 14 (discharge dependent). As per ischemia stroke criteria, a change ≥ 4 in the NIHSS will be considered a neurologic change and will be followed over time.
 - Additionally, during hospitalization and at all follow up visits, we will monitor for all drug related and other adverse events, not limited to hepatic function, in-hospital mortality, 30-day mortality, 90-day mortality, and all-cause mortality.

IV. Outpatient follow-up:

Follow-Up Visit 1 (30 ± 14 days after admission)

Standard of care in-person follow up visit to assess neurologic status and functional recovery based on the outcome measures above. At this time, a standard of care Neuroimaging of the brain will be done to follow the resolution of perihematomal edema and to assess for delayed hydrocephalus. 10 cc of blood will also be drawn for standard of care studies (CBC with differential and lymphocyte subset analysis, CMP), in addition to 5 cc set aside in storage for future multi-omic analysis. Any potential long-term drug adverse effects are to be followed at this time.

Follow-Up Visit 2 (90 ± 14 days after admission)

Standard of care in-person follow up visit to assess neurologic status and functional recovery based on the outcome measures above. At this time, there will be a standard of care Neuroimaging of the brain to follow the resolution of both the hematoma and perihematomal edema. Any potential long-term drug adverse effects will be followed at this time.

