Follow-Up Visit 3 (180 ± 14 days after admission)

In-person follow up visit to assess neurologic status and functional recovery based on the outcome measures above. Any potential long-term drug adverse effects will be followed at this time. At this time, there will be a Neuroimaging of the brain to follow the resolution of both the hematoma and perihematomal edema. Any potential long-term drug adverse effects will be followed at this time

Follow-Up Visit 4 (365 ± 14 days after admission)

In-person follow up visit to assess neurologic status and functional recovery based on the outcome measures above. Standard of care Neuroimaging will be performed to assess brain injury and atrophy.

	Enrollment	24 hrs post -	72 hrs post - ictus	5-7 days	10-14 days	Discharge	30±1 4 days	90±14 days	180±14 days	365±1 4 days
--	------------	---------------	---------------------	----------	------------	-----------	-------------	------------	-------------	--------------

		ictus +									
Neuroimaging Diagnostic CT,CTA,MRA or MRI	X	X	X	X	X [‡]			X	X	X	X
Medical history	X										
ICH score	X										
EKG	X										
Speech and swallow evaluation	X										
Informed consent	X										
Single drug dose (fingolimod or placebo)	X										
CSF*	X*	X*	X*	X*	X*						
Peripheral whole blood (CBC, CMP, lymphocyte subsets)	X	X	X	X	X [‡]			X			
Telemetry	X	X	X								
Vital signs	X	X	X	X	X			X	X	X	X
Neuro exam	X	X	X	X	X			X	X	X	X
NIHSS	X	X	X	X [†]	X [†]	X	X	X	X	X	X
mRS	Historic			X [†]	X [†]	X	X	X	X	X	X
PROMIS 10				X [†]	X [†]	X	X	X	X	X	X
MoCA				X [†]	X [†]	X	X	X	X	X	X
WAB-R				X [†]	X [†]	X	X	X	X	X	X

* If the participant requires EVD placement.

†Or at time of discharge

‡ If still hospitalized or clinically indicated

+ At least 6 hours after medication given

Outcome Measures:

Primary outcome measure:

- Safety of a single-dose administration of fingolimod to critically ill patients. We will be assessing rates of the following adverse events:
 - Clinically significant cardiac events at 30 days
 - Nosocomial infections (UTI, sepsis, and pneumonia) at 90 days
 - Neurologic decline, considered a change ≥ 4 points of the NIHSS at 30 days

Secondary outcome measures:

- Feasibility of administering fingolimod through an NGT or Dobhoff tube.
- Changes seen in the lymphocyte subpopulations at 30 days. The lymphocyte subsets of CD4+ T, CD8+ T, and CD19+ B cells will be compared among the three groups and the trends will be followed over time in all participants.

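### The cardiac safety outcome is planned only as an event rate, and no comparison by arm is planned for the early heart-rate fall that the protocol itself expects

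*Combined protocol and SAP*

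**What the plan says.** Under III. Adverse events, the protocol describes the drug's expected cardiac effect, its timing, and a rate for the clinical consequence: "Maximal decrease in heart rate occurs within 6 hours of drug administration and recovers, with only 0.5% of patients experiencing clinically symptomatic bradycardia". The rationale at the end of section 1.5 gives the same figure: "the incidence of clinically significant bradycardia after the first dose has been reported in 0.5" per cent. Both statements concern bradycardia.

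The primary outcome list words the cardiac component as "Clinically significant cardiac events at 30 days". No event types or thresholds are listed.

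On data capture, III. Adverse events states: "All subjects will be placed on telemetry for 72 hours after administration of drug and changes in heart rate or rhythm will be recorded". Section II of Interventions and Interactions adds, on vital signs: "Vitals will be specifically recorded at the time of their neurologic assessment by the blinded assessors". In the schedule of assessments, vital signs are marked at Enrollment and next in the 24-hour post-ictus column. The footnote to that column reads "At least 6 hours after medication given".

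Aim 1 under Statistical Analysis estimates event rates with 95% CIs in the study groups and sets them against historical rates where these exist. Heart rate does not appear as a variable there or among the secondary outcomes.

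**The concern.** The protocol names one specific cardiac effect of the drug, says when it peaks, and runs a monitor through that period. The planned analysis then keeps only whether a clinically significant event occurred. For an outcome as rare as the cited bradycardia rate, a group of 10 to 25 treated patients will usually show none, whether heart rate falls by a little or a lot on average.

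The Aim 1 text says its comparisons help to ensure that adverse event rates are not elevated. For bradycardia, a count of this size cannot carry that weight. The trial would also finish without an estimate of the size or variability of the heart-rate effect in ICH patients, which a pilot meant to inform the design of a later trial could supply from data it already collects.

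**Working it through.** **Inputs from the documents**
- Reference rate for bradycardia: 0.5% (section 1.5 rationale; III. Adverse events).
- Total sample 30, with 10 open-label fingolimod patients (Sample Size). The text does not settle whether the 10 are inside the 30.
- Equal allocation in the randomized part (Randomization).

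If the 10 are inside the 30, randomized fingolimod n = (30 − 10)/2 = 10, and all fingolimod n = 10 + 10 = 20. If they are additional, the figures are 30/2 = 15 and 15 + 10 = 25.

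There is no planned figure to reproduce: the sample size is stated without an effect size, power or precision target.

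**Step 1. What a bradycardia count would show**

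P(no events) = (1 − 0.005)^n. The exact two-sided 95% upper limit after zero events is 1 − 0.025^(1/n).

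| Fingolimod patients | Expected events | P(zero) at 0.5% | Upper limit after zero |
|---|---|---|---|
| 10 | 0.050 | 95.1% | 30.8% |
| 15 | 0.075 | 92.8% | 21.8% |
| 20 | 0.100 | 90.5% | 16.8% |
| 25 | 0.125 | 88.2% | 13.7% |

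The upper limits are about 27 times (13.7/0.5) to 62 times (30.8/0.5) the reference rate. To have a 95% chance of seeing one event at 0.5%, about ln(0.05)/ln(0.995) = 598 treated patients would be needed.

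**Step 2. Sensitivity to a broader event definition**

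The outcome covers cardiac events generally over 30 days, and the documents give no rate for that. At an assumed 5%, P(zero) is 0.95^10 = 59.9% and 0.95^20 = 35.8%. At an assumed 10%, it is 34.9% and 12.2%. The result in Step 1 therefore applies to the bradycardia component, not to the whole outcome.

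**Step 3. What falls in the first 6 hours**
- Expected effect: maximal within 6 hours.
- Telemetry: covers the window, with changes recorded.
- Scheduled vital signs: one reading at Enrollment, then none until at least 6 hours after dosing.
- Scheduled EKG: Enrollment only.
- Planned summary by arm: none.

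The gap is in the analysis. The data source exists.

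**Step 4. What a continuous measure would give**

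The unadjusted 95% CI half-width for an arm difference is t(0.975, 2n − 2) × SD × √(2/n). The documents give no SD, so 8 to 15 bpm is assumed. For example, at 10 per arm and SD 8: 2.101 × 8 × √0.2 = 7.5.

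| Assumed SD (bpm) | 10 per arm | 15 per arm |
|---|---|---|
| 8 | 7.5 | 6.0 |
| 10 | 9.4 | 7.5 |
| 12 | 11.3 | 9.0 |
| 15 | 14.1 | 11.2 |

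The difference detectable with 80% power (noncentral t, two-sided 0.05) runs from 10.6 to 19.9 bpm at 10 per arm and from 8.5 to 15.9 bpm at 15 per arm.

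**The case against.** Four stronger readings are tempting, and the documents do not support them.

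- A reader might infer that the whole cardiac outcome will almost surely be zero. The 0.5% is for bradycardia. The outcome is wider and has no stated rate, and Step 2 shows that zero is far from certain at plausible higher rates.
- A reader might infer that vital signs are recorded only after the effect has passed. There is an Enrollment reading, and standard-of-care vital signs continue between the scheduled assessments. Only the first scheduled post-dose reading falls at or after 6 hours.
- A reader might infer that heart rate is never looked at. Data and Safety Monitoring lists EKGs and vital signs for routine review. Adverse event reporting requires an AE for any vital-sign or EKG worsening that the investigator judges clinically significant. An important slowing therefore has a route into the reported rates. That route passes on an event and a judgement, though, not the size of the change by arm.
- A reader might conclude that the event rate should be dropped or reduced to a listing. That would change the safety question set by Specific Aim 1, and the gap does not require it.

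The remaining objections have more weight. Wide limits after zero events are common to any pilot of this size, and the plan acknowledges its small samples. The proposed measure would detect only a fairly large mean fall, and a mean difference is not itself a measure of clinical harm. The protocol says that changes will be recorded but not that the traces are kept, so the lowest value may not be retrievable later. These points limit what the measure can claim. They do not remove the case for prespecifying an estimate of the one cardiac effect that the protocol names.

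**Conclusion.** The point holds in a limited form. The plan captures heart rate through the period in which it expects the drug's effect, but it plans no comparison of heart rate between arms. For bradycardia, the event count is likely to be zero (88% to 95%) and, if so, still leaves an upper limit of about 14% to 31%.

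The count figures assume that the 0.5% rate carries over to these patients, and they cover both readings of whether the open-label patients are within the 30. The half-widths for heart rate (7.5 to 14 bpm at 10 per arm, 6 to 11 bpm at 15 per arm) rest wholly on the assumed SD. The gap weakens what the primary safety aim can report. It does not invalidate the event rate as an outcome.

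**What to change.** Keep the rate of clinically significant cardiac events at 30 days as the primary cardiac outcome. Add to Aim 1 under Statistical Analysis, as a prespecified supportive safety measure, the pre-dose heart rate minus the lowest telemetry heart rate in hours 0 to 6 after dosing. Report the fingolimod-minus-placebo difference among randomized participants with a 95% CI, adjusted for pre-dose heart rate. Describe the open-label group separately, since it is not randomized. State in the text that precision is limited and that the measure estimates the effect and does not establish safety.

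The cost is two values per participant, extracted from telemetry that is already running. Extraction must happen while recordings are retrievable. A single lowest value is open to artefact, so the rule for accepting a reading should be written down before unblinding. No change to dosing, monitoring or patient management is involved.

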1.1 Overview

Spontaneous intracerebral hemorrhage (ICH) is a catastrophic illness representing a global public healthcare problem. Unfortunately, there currently exists no specific treatment outside of supportive medical care. Of the 15 million strokes reported worldwide per annum, ICH accounts for approximately 10-15% of all stroke cases in the US, Europe and Australia; and approximately 20-30% of strokes in Asia.¹ This is associated with a 40% 30-day mortality rate², and those who survive have major neurologic deficits, with only around 20% of patients reaching functional independence at 6 months.³ Although there has been a significant reduction in overall age-adjusted incidence of stroke, the incidence of ICH has remained unchanged in the past 40 years.² In the US alone, the annual healthcare costs of ICH is estimated at \$12.7 billion.⁴

Hospitalizations for ICH have increased by 18% in the last decade⁵, most likely due to the aging population and the increasing use of anticoagulants, thrombolytics, and antiplatelet agents. The most important risk factor is age. With each advance in decade after the age of 50, there is a 2-fold increase in ICH incidence.⁶ ICH due to hypertension (HTN) accounts for approximately 65% of all spontaneous ICH⁷ and 50-70% of patients are hypertensive at the time of hemorrhage.⁸ ICH in the setting of HTN commonly occurs in the deep cerebral locations (basal ganglia, thalamus), followed by cerebral lobes, cerebellum, and brainstem (predominantly pons).⁶ ICH occurring in the setting of cerebral amyloid angiopathy almost always present in a lobar location. Other causes of ICH include neoplasms, aneurysms, arteriovenous malformations (AVM), cerebral cavernous malformations, arteriovenous fistulae (AVF), and venous thrombosis.⁷

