Study Design: We propose a randomized, double-blinded, placebo-controlled pilot trial of fingolimod in patients with primary spontaneous intracerebral hemorrhage. Eligible participants will be allocated to study groups using fixed allocation randomization and a computer-based random number-generating allocation. Allocation will be equal. For those patients who meet all inclusion criteria without exclusion criteria subjects will receive oral or nasogastric tube (NGT) or Dobhoff feeding tube administration of fingolimod versus placebo. Participants will be monitored at time of enrollment and days 1, 3 5, 7, and 14 (discharge dependent) by 2 blinded assessors (neuroscience subspecialists) and will receive standard of care for the duration of the study. After discharge from the hospital, participants will enter a follow up phase of 12 months, with clinic visits at 30 ± 14 days, 90 ± 14 days, 180 ± 14 days, and 365 ± 14 days. They will receive a standard of care Neuroimaging at these follow up time-points day visit and will be assessed with the pre-selected outcome assessments established by the NINDS Common Data Elements for Stroke.

Laboratory studies: We will perform standard of care CBC with differential and flow cytometry to follow numbers of T helper cells, cytotoxic T cells, B cells, and macrophages in peripheral blood to assess the viability of these levels as a biomarker of drug effect.

Cells isolated from the peripheral blood or CSF will be incubated with a panel of antibodies to identify the following immune populations: CD4+ T cells: CD4+CD3+ and Tbet (Th1), GATA-3 (Th2), ROR \square T (Th17) FoxP3 (Treg); CD8+ T cells: CD8+CD3+T-bet; CD19+ B cells; M1:CD68+CD163-CD80+CD64+; M2:CD68+CD163+CD206+TGM2+

Additional markers of activation/differentiation tested include P2Y12, S1PR1, S1PR5, PD-1. Cells will be washed and analyzed using the BD Fortessa flow cytometric analysis instrument. In some cases, populations will be isolated for further analysis by fluorescence-based cell sorting.

With the use of commercially available assays, quantification of the top 5-10 cytokines that are present in the peripheral blood will also be performed.

We will store all CSF and blood samples to perform future Next-Gen multi-omic analysis of all CSF and blood samples including: mRNA-seq, SPLiT-seq, antibody fluorescent, DNA methylation, and mass spectroscopy. Future laboratory study procedures as detailed below.

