DNA will be isolated from the blood and CSF using standard protocols currently performed in [name] laboratory. DNA will be bisulfite-converted using the EZ DNA Methylation Gold kit (Zymo, Irvine, CA), as performed routinely in our laboratory. This kit is designed to work with a wide range of DNA amounts, ranging from 500 pg to 2 µg of DNA. Bisulfite treatment of DNA converts all non-methylated cytosines in the genomic DNA to uracil, whereas methylated cytosines remain unchanged. To determine the proportion of DNA methylation at each site, we will use the Infinium MethylationEPIC BeadChip (Illumina, Inc.), which targets approximately 850,000 CpG sites at single-nucleotide resolution, and the HiScan Reader (Illumina, Inc.). This microarray assays CpG sites from RefSeq genes, including the promoter, 5' UTR, first exon, gene body, and 3' UTR. The proportion of methylation for each site is based on the ratio of the fluorescence intensity of the methylated versus the combined methylated and unmethylated probes (referred to as the beta value), and will be determined with GenomeStudio (Illumina, Inc.). A ratio value of 0 equals no methylation of the locus and a ratio of 1 equals total (100%) methylation.

Setting: The study will occur at Wake Forest Baptist Medical Center during the patient’s hospitalization through admission, operation, Neurosciences Intensive Care Unit stay, Neurology/Neurosurgery floor stay, and outpatient follow up in the neurosurgical clinic. The duration of the study for each participant will be approximately 12 months.

Subjects selection criteria:

All adult patients ages 18-80 who present to Wake Forest Baptist Medical Center with the diagnosis of spontaneous intracerebral hemorrhage.

• **Inclusion Criteria**

- Has given written informed consent to participate in the study in accordance with required regulations; if a participant is not capable of providing informed consent, written consent must be obtained from the participant’s legally authorized representative (LAR). When the LAR is not available for consent, Docusign for econsent may be obtained.

- Stated willingness to comply with all study procedures and availability for the duration of the study.
- Men and non-pregnant women ages 18-80 years old

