- If an EVD is present, the drain output will be collected daily as part of standard of care. On Day 1, 3, 5, 7, 10, and 14 after placement, 5 cc at each time point will be collected and 4 cc to be sent off for standard of care infectious surveillance and 1 cc to be saved for future multi-omic analysis. The EVD will be removed in a standard fashion based on the clinical and radiographic determination that the participant no longer has hydrocephalus. If a patient undergoes EVD removal if clinically indicated prior to the Day 10 or 14 collection time points, they will not undergo these final CSF draws.
- Each participant will undergo a standard of care Neuroimaging of the brain 24 hrs and 5-7 days, 90 days, 180 days and 365 days after drug administration to assess the stability and resolution of the hemorrhage, follow the perihematomal edema, evaluate for evidence of hydrocephalus, and the development of subsequent brain atrophy that occurs after ICH. There will be a standard of care Neuroimaging on day 14 if the participant is still hospitalized or clinically indicated.
- 72 hours after admission, each participant will undergo a standard of care non-contrast Neuroimaging of the brain to assess the extent of perihematomal edema after drug administration. There will also be a standard of care Neuroimaging at the 30 day follow up to follow the resolution of hematoma and perihematomal edema. All radiographic data will be used to calculate volumetric measurements via RAPID protocol to measure hematoma and perihematomal edema volume.
- Each participant will undergo standard of care speech, cognitive, physical, and occupational therapy to be initiated upon admission. At time of discharge, post-ICH reference outcome measures established by the NINDS Common Data Elements for Stroke are to be performed and recorded. These will include interviewer-administered modified Rankin Scale (mRS), patient-reported PROMIS 10, Montreal Cognitive Assessment (MoCA), and the Western Aphasia Battery-Revised. These outcome measures will assess for various aspects of recovery, including physical, emotional, and neurocognitive. These clinical assessments will also be performed and recorded at the time of discharge, and at the 30, 90, 180, and 365 day visits. We will also be collecting each participant's disposition at time of discharge, 30, 90, 180, and 365 days.

III. Adverse events:

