- All radiographic imaging performed (CT and MRI) will undergo volumetric measurement calculations of hematoma and perihematomal volumes via RAPID protocol. These volumes will be correlated with biomarker levels of inflammatory cells and clinical outcome assessments.
- NIHSS at 365 days post-ictus.
- *Interviewer-administered modified Rankin Scale score at 365 days post-ictus.*
- Patient-Reported Outcomes Measurement Information System 10 at 365 days (patient report of physical and neurobehavioral function). As referenced in the ICF, all these outcomes measures will be done in the context of a standard of care visit. If any participant endorses symptoms consistent with depression or are at risk of causing harm to self and others, we will follow the institutional policy regarding making the appropriate referral to their primary physician to address these concerns or appropriate psychiatric referral.
- Montreal Cognitive Assessment (MoCA) at 365 days post-ictus.
- Western Aphasia Battery – Revised (WAB-R) at 365 days post-ictus.
- Mortality at 30 days
- Mortality at 90 days
- All cause mortality within the study period
- Patient disposition: number of home days over 365 days
- Multi-omic analysis of inflammatory phenotypes related to ICH

Analytical Plan:

Randomization:

Randomization of the study participants should occur after the participant has undergone eligibility screening and has been consented if all criteria have been met. Consented participants will be allocated to study groups using fixed allocation randomization and a computer-based random number-generating allocation. Allocation will be equal. The study pharmacist will be the only unblinded member of the study and will provide the appropriate study agent based on the statistician's randomization schema. Enrollment into the open-label arm of fingolimod will not be randomized.

Statistical Analysis:

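### After discharge, disability scales are tied to in-person clinic visits with no remote or proxy fallback, so the later estimates can overstate recovery if disabled survivors attend less often

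*Combined protocol and SAP*

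**What the plan says.** Study Design sets the follow-up: "After discharge from the hospital, participants will enter a follow up phase of 12 months, with clinic visits at" 30, 90, 180 and 365 days, each ±14 days. Setting places it as "outpatient follow up in the neurosurgical clinic". Under IV. Outpatient follow-up all four visits are in person; the entries for Visits 3 and 4 read "In-person follow up visit to assess neurologic status and functional recovery based on the outcome measures above".

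Part II of Interventions and Interactions lists the mRS, PROMIS-10, MoCA and WAB-R and says "These clinical assessments will also be performed and recorded at the time of discharge, and at the 30, 90, 180, and 365 day visits". The schedule table adds the NIHSS at the follow-up visits and also places the scales in hospital at 5-7 and 10-14 days. The secondary outcomes include "Interviewer-administered modified Rankin Scale score at 365 days post-ictus" and "Montreal Cognitive Assessment (MoCA) at 365 days post-ictus", with the NIHSS, PROMIS-10 and WAB-R at the same time point.

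III. Adverse events puts monitoring of adverse events and mortality in the hospital stay and at the follow-up visits. Disposition is collected at the same days without being tied to a visit.

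No telephone, video, home, caregiver or facility assessment is described. Aim 3 under Statistical Analysis gives no denominator and does not say how a death or a missed visit enters a scale. The only mention of missing data is a caution under Aim 2.

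**The concern.** Severe disability is itself a reason to miss a clinic visit. The protocol expects a badly affected population: section 1.1 says ICH is "associated with a 40% 30-day mortality rate", with "only around 20% of patients reaching functional independence at 6 months". A bedbound participant, or one in a distant facility, may have no mRS at day 180 or 365, although an mRS interview need not take place in a clinic.

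Aim 3 uses these data to estimate the percentage of patients benefiting, and the variability and correlations that will inform a future sample size. It also hypothesises that improvement will be clearer at 180 days than at 90 days. If dependent survivors drop out of view as time passes, an apparent gain between those visits could arise without any real change. Safety data are exposed as well: nosocomial infection is a primary outcome counted to 90 days, and for participants discharged earlier the follow-up visit is the scheduled point of enquiry.

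**Working it through.** **The plan's own figure.** There is none to reproduce. The documents give no attendance, dropout or expected disability figure, and the total of 30 participants is justified as a pilot without statistical inputs.

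**Inputs.**
- From section 1.1: 40% mortality at 30 days and about 20% independent at 6 months.
- The 20% can be read as a share of all patients or of survivors. On the first reading, the share among survivors is 0.20 / (1 − 0.40) = 0.333, treating the 30-day mortality as if it held at 6 months. On the second it is 0.20.
- Assumed, with no source in the documents: attendance of independent survivors (*a*) and of dependent survivors (*b*).

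**Effect of attendance.** With *p* the true independent share among survivors, the share seen among attenders is

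p·a / (p·a + (1 − p)·b).

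| p | a | b | Calculation | Observed share |
|---|---|---|---|---|
| 1/3 | 0.95 | 0.80 | 0.317 / (0.317 + 0.533) | 37% |
| 1/3 | 0.95 | 0.60 | 0.317 / (0.317 + 0.400) | 44% |
| 0.20 | 0.95 | 0.80 | 0.19 / (0.19 + 0.64) | 23% |
| 0.20 | 0.95 | 0.60 | 0.19 / (0.19 + 0.48) | 28% |
| 1/3 | equal to b | equal to a | the attendance cancels | 33% |
| 1/3 | 0.75 | 1.00 | 0.25 / (0.25 + 0.667) | 27% |

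The first four rows show upward bias of 3 to 11 percentage points. The fifth shows none, and the last shows the reverse. The first two rows also bear on the 90- versus 180-day hypothesis: if *b* fell from 0.80 to 0.60 between those visits, observed independence would rise from 37% to 44% with no true change.

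**Effect of the denominator.** Take the all-patients reading and full attendance. If only living participants were counted, the share would be 0.20 / (1 − m), where *m* is mortality:
- m = 10%: 22%
- m = 20%: 25%
- m = 30%: 29%
- m = 40%: 33%

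The range below 40% is an assumption, because eligibility should lower the rate. If an arm has 10 participants, the chance of at least one death is 1 − 0.9^10 = 65% even at 10% mortality. So a rule for deaths will very probably be needed.

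**The case against.** Much can be said for the plan. The scales are also done in hospital and at discharge, so a non-attender is not without data. Mortality, disposition and days at home over the year are separate outcomes. Participants may volunteer adverse events, and serious events must be reported within one working day of awareness through day 365 whether or not a visit takes place. These routes would partly expose selective loss. The visits include neuroimaging, so there is a reason for attendance in person. The outcomes are secondary, in a small pilot that describes its own samples as small. With 6 independent of 18 survivors the exact 95% interval is 13% to 59%, wide against a shift of 3 to 11 points.

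All of this stands. It limits the consequence but does not supply a day-180 or day-365 mRS for a participant who cannot travel. Imprecision is not an answer either, because a systematic shift passes into the planning values for the next trial.

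A reader might go further and infer that the day-365 scales are planned as averages over survivors, that they will describe the healthiest participants, or that the arm comparison is biased. The documents do not support this. Aim 3 names no mean and no survivor restriction; its denominator is simply undefined. There are no attendance data, so the direction is not established. Bias in the difference between fingolimod and placebo would need death or attendance to differ by arm. The 40% mortality is a general ICH figure, and the exclusions (GCS of 4 or less, brainstem hemorrhage, DNR/DNI status, co-morbidities limiting one-year survival) should lower it by an unknown amount.

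**Conclusion.** The point holds as a gap in data collection. Post-discharge disability scales depend on in-person attendance, no fallback is given, and the loss is plausibly related to outcome. The bias is possible but not demonstrated: on assumed attendance rates it runs from nil to about 11 points upward, and it could run downward if independent survivors were the ones to stay away. The calculation concerns the level of recovery within a group and says nothing about a treatment difference.

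The treatment of deaths in the mRS and the Aim 3 denominator are missing detail to be written in; they are not errors in a stated analysis. This is a worthwhile, inexpensive improvement to secondary outcomes and to safety follow-up. It does not undermine the pilot's purpose.

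**What to change.** **In IV. Outpatient follow-up**, add that when a participant cannot attend, the following are obtained within the visit window by telephone or video, or from a caregiver or facility, with the mode recorded: the mRS interview, PROMIS-10 where the instrument allows, disposition, adverse events and vital status.

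**In Aim 3 under Statistical Analysis**, state that:
- deaths count as mRS 6 and stay in the mRS denominator;
- NIHSS, MoCA, PROMIS-10 and WAB-R are summarised in survivors and shown beside mortality;
- the numbers dead and not assessed are given by arm at each visit.

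No rank test that places deaths below survivors on the other scales is needed. The Wilcoxon test is specified only for the Aim 2 biomarkers, and Aim 3 is descriptive.

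The cost is some coordinator calls and a few sentences of protocol text. The drawback is mixed assessment modes for the mRS, which recording the mode makes visible. NIHSS, MoCA and WAB-R may still be missing for participants who cannot attend, and the counts of those not assessed will show how many.
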